3.4.3. Concomitant Vaccines and Medications

Specific concomitant vaccines will be collected as indicated in the protocol and recorded in the CRF. Concomitant medications will be recorded only if they are used to treat SAEs. Concomitant vaccines and medications will be coded using the WHO DDE.

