1.3. Schedule of Activities

The SoA table provides an overview of the protocol visits and procedures. Refer to the **STUDY ASSESSMENTS AND PROCEDURES** section of the protocol for detailed information on each procedure and assessment required for compliance with the protocol.

The investigator may schedule visits (unplanned visits) in addition to those listed in the SoA table, in order to conduct evaluations or assessments required to protect the well-being of the participant.

Visit Number	1	2
Visit ID	Vaccination	Follow-Up Visit
Visit Window (Days)	Day 1	28 to 42 Days After Visit 1
Visit Type	Clinic Visit	Clinic Visit
Obtain informed consent	X	
Assign participant number via IRT	X	
Obtain demography and medical history data	X	
Measure height and weight	X	
Perform clinical assessment ^a	X	
Review prior vaccination history to confirm participants are naïve to pneumococcal vaccines	X	
Record concomitant nonstudy vaccinations and concomitant medications used for treatment of SAEs	X	X
Obtain prevaccination oral temperature	X	
Perform pregnancy test (if appropriate)	X	
Contraception check (if appropriate)	X	
Review inclusion and exclusion criteria	X	
Obtain blood sample for immunogenicity assessment of OPA titers (~30 mL) ^b	X ^c	X
Administer study intervention	X	
Observe and record acute reactions for 30 minutes after 20vPnC administration	X	
Provide participant with an e-diary (device or application, if used), digital thermometer, and measuring device and instruct to collect prompted local reactions and systemic events for 7 days after vaccination	X	
Provide a participant contact card	X	
Review e-diary data (daily is optimal during 7-day diary period)	X-----X	

Visit Number	1	2
Visit ID	Vaccination	Follow-Up Visit
Visit Window (Days)	Day 1	28 to 42 Days After Visit 1
Visit Type	Clinic Visit	Clinic Visit
Review e-diary symptoms with participant and obtain stop dates where applicable		X
Collect e-diary or assist the participant to delete the application, if applicable		X
AEs and SAEs collection	X-----X	

Abbreviation: IRT = interactive response technology

- a. Including, if indicated, a physical examination.
- b. Immunogenicity subset only: Blood will be drawn in the first approximately 50 participants in each age cohort (18 to 49 years of age and \geq 50 years of age) for a study total of approximately 100 participants (approximately 25% of all participants).
- c. Blood sample will be collected prior to vaccination.

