6.8. Concomitant Therapy

6.8.1. Prohibited During the Study

- Receipt of any investigational vaccines, drugs, or medical devices is prohibited during study participation.
- Receipt of nonstudy pneumococcal vaccine is prohibited during study participation.
- Receipt of any other licensed nonstudy vaccine is prohibited during the study, unless medically necessary (see [Section 6.8.2](#)).
- Receipt of blood/plasma products, immunoglobulins, monoclonal antibodies, radiotherapy, and/or immunosuppressive therapy (including a ≥ 14 -day course of systemic corticosteroids) is prohibited during study participation.

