6.9. Recording Prior and Concomitant Vaccines and Concomitant Treatments

The name and date of administration for all nonstudy vaccinations received from the time of signing of the ICD to Visit 2 will be collected and recorded in the CRF.

Medications taken to treat SAEs from the time of signing of the ICD to Visit 2 will be recorded in the CRF.

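### Does recording only SAE treatments leave the evaluable immunogenicity set without a check for therapies prohibited during the study?

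*SAP*

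**What the plan says.** Protocol 6.8.1 lists what participants may not receive after vaccination. Besides vaccines it names "Receipt of blood/plasma products, immunoglobulins, monoclonal antibodies, radiotherapy, and/or immunosuppressive therapy", with a qualifier on systemic corticosteroid courses of 14 days or more. It also says: "Receipt of any investigational vaccines, drugs, or medical devices is prohibited during study participation".

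The recording rules are narrower. Protocol 6.9 collects "The name and date of administration for all nonstudy vaccinations received from the time of signing of the ICD to Visit 2", whatever the reason for vaccination. For medicines it says: "Medications taken to treat SAEs from the time of signing of the ICD to Visit 2 will be recorded in the CRF". The Schedule of Activities has one row for both, marked at both visits: "Record concomitant nonstudy vaccinations and concomitant medications used for treatment of SAEs". Protocol 4.1 and 8.9.2 repeat this scope, and SAP 3.4.3 puts it most firmly: "Concomitant medications will be recorded only if they are used to treat SAEs".

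The Schedule row "Review inclusion and exclusion criteria" is marked at Visit 1 only. The synopsis says the one-month visit also looks at whether participants remain eligible. That step is absent from the Schedule, 4.1 and 8.9.2.

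The evaluable immunogenicity set (protocol 9.2, SAP 4) drops participants whom the clinician finds to have another major deviation. Protocol 9.1.1 frames the immunogenicity estimand as hypothetical: the effect if everyone followed the protocol.

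**The concern.** An exclusion rule is only as good as the information behind it. Suppose a participant in the immunogenicity subset received immunoglobulin, or a long steroid course, for something that was not an SAE. The routine medication record would not show it. Exclusions 11 and 12 ask at Visit 1 about planned receipt, which cannot reveal what was given later. The participant could then stay in the GMFR analysis, and whether the clinician learned of the therapy would depend on how it surfaced. The start and stop dates needed to apply the steroid qualifier are not routinely requested either.

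At stake is the secondary endpoint: the fold rise in OPA titers in about 50 participants per age cohort, under an estimand that assumes adherence. The synopsis phrase adds to the impression of an omission, because it suggests that a check was intended and then lost.

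**Working it through.** **Coverage.** The plan states no figure to reproduce here, so the first step sets the 6.8.1 categories beside the Visit 2 procedures.

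| Category in protocol 6.8.1 | Asked of everyone at Visit 2? | In-study clause in exclusion criteria (5.2) | Other routes |
|---|---|---|---|
| Nonstudy vaccines | Yes, name and date (6.9) | Criterion 9, pneumococcal only | Not needed |
| Investigational drugs or devices | No | Criterion 13 | AE follow-up, monitoring |
| Blood/plasma products, immunoglobulins | No, unless treating an SAE | Criterion 12 | AE follow-up, monitoring |
| Immunosuppressive therapy | No, unless treating an SAE | Criterion 11 | AE follow-up, monitoring |
| Monoclonal antibodies | No, unless treating an SAE | None named | AE follow-up, monitoring |
| Radiotherapy | No | None named | AE follow-up, monitoring |

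The gap in direct questioning is real. For radiotherapy and devices, which are not medications, the recording rule is silent rather than restrictive.

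**How a prohibited therapy would come to light.**

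1. Entry requires any pre-existing disease to have been stable for 12 weeks (5.1). It excludes immune deficiency, current immunosuppression and serious chronic disorders (5.2). A therapy newly started within 28 to 42 days would therefore usually follow a new or worsened condition.
2. Such a condition is an AE under 10.2.1, which includes worsening of a chronic condition.
3. Each participant is questioned about AEs (8.3), and 8.9.2 repeats this at Visit 2.
4. For each event, 8.3.3 requires relevant information to be supplied, including concomitant medications. This is not confined to SAEs.
5. Monitors verify source data and protocol compliance, and current medical records must be available (10.1.8).
6. Protocol 7.2 lists both protocol deviation and loss of eligibility among the reasons for discontinuation.

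The route is indirect and does not guarantee dates, but it starts from a question put to everyone.

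**Effect of a missed case.** The documents give no rate of prohibited therapy and no effect on titers, so r, k and the SD below are assumptions. The cohort size n = 50 is from protocol 9.5.

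If k of n participants have a fold rise r times that of the others, the GMFR is multiplied by r^(k/n).

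| r | k = 1, n = 50 | k = 1, n = 100 (cohorts pooled) |
|---|---|---|
| 0.5 | 0.986 (-1.4%) | 0.993 (-0.7%) |
| 0.1 | 0.955 (-4.5%) | 0.977 (-2.3%) |
| 2 | 1.014 (+1.4%) | 1.007 (+0.7%) |
| 10 | 1.047 (+4.7%) | 1.023 (+2.3%) |

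Number of participants needed for a 10% fall at n = 50: k = 50 × ln(0.9)/ln(r).

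- r = 0.5: k = 7.6, so 8 participants (factor 0.895).
- r = 0.1: k = 2.3, so 3 participants (factor 0.871).

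Sampling precision: the 95% half-width on the ln scale is t × SD/√n, with t(0.975, 49 df) = 2.010.

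- SD 1.0: 2.010 × 1.0/√50 = 0.284, so the interval is -24.7% to +32.9%.
- SD 1.5: 2.010 × 1.5/√50 = 0.426, so the interval is -34.7% to +53.2%.

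One participant shifts the mean ln fold rise by |ln r|/50, which is 0.0139 (r = 0.5) or 0.0461 (r = 0.1). That is 4.9% or 16.2% of 0.284, and 3.3% or 10.8% of 0.426. One missed case therefore moves the estimate by 3% to 16% of the CI half-width.

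**The case for a change.** The best case for a change is that the protocol treats similar deviations unequally. Vaccines are asked about in everyone, with dates, while the other categories are left to AE follow-up and monitoring. Asthma and COPD are among the conditions recorded at entry (8.9.1), so a steroid course for a nonserious flare is plausible. One of 14 days or more fits inside the follow-up interval. Source verification may miss care given elsewhere if nobody asks. Adding a question for about 100 participants seems cheap, and the synopsis already promises some such review.

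Part of this stands. Direct ascertainment is uneven, and the synopsis does not match the Schedule, 4.1 and 8.9.2. The broader wording for telehealth visits in 10.6.1 does not close the gap, since it applies only when clinic visits cannot take place.

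The rest is weaker. The flare in the example is itself an AE, so it falls within universal questioning and 8.3.3. Receipt of a prohibited therapy is not automatically a major deviation: the clinician decides, and the participant might properly remain in the set. A question on each 6.8.1 category, with dates, is several CRF fields. It also goes beyond an eligibility review, because monoclonal antibodies and radiotherapy are not named in the eligibility criteria. It would need an amendment with IRB/EC approval (10.1.1), and participants already past Visit 2 would lack the data.

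**Conclusion.** No change to the plan is needed. Limiting the medication record to SAE treatments is a deliberate choice, stated consistently in the Schedule of Activities, protocol 4.1, 6.9 and 8.9.2, and SAP 3.4.3. It is a fair trade-off for a single-dose descriptive study, given universal AE questioning, event follow-up and monitoring. Analysts can build the evaluable set from the deviations those routes supply.

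Under the assumptions above, one missed case in a cohort of 50 changes the GMFR by between -4.5% and +4.7%, well inside the confidence interval. A 10% fall would need several missed cases in one cohort: 8 at half the fold rise, or 3 at one tenth. Nothing in the documents suggests that frequency. The endpoint is secondary and descriptive, no hypothesis is tested, and the safety set does not use the deviation exclusion.

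The synopsis phrase is a clerical slip that can be tidied if the protocol is reopened for another reason; it alters no analysis. The conclusion assumes that prohibited therapy is rare in this stable population and that deviation reporting works in the ordinary way. The CRF completion guidance and the monitoring and data management plans, which govern that reporting, were not available to check.

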3.5. Safety Endpoints

Local reactions, systemic events, AEs, and SAEs have been described above in the primary endpoints.

4. ANALYSIS SETS (POPULATIONS FOR ANALYSIS)

Analysis populations are defined for the statistical analysis of safety results in the table below.

Population	Description
Enrolled in the study	All participants who signed an ICD.
Assigned to study intervention	All participants who are assigned an enrollment number in the IWR system.
Safety	All participants who receive any study intervention and have safety data assessed after vaccination.
Evaluable immunogenicity	All eligible participants in the immunogenicity subset who receive 1 dose of the study intervention with at least 1 valid immunogenicity result from the blood sample collection within 27 to 49 days after vaccination and have no other major protocol deviations as determined by the clinician.
CCI	

E-diary data will be summarized among those in the safety population who report any e-diary data.

5. GENERAL METHODOLOGY AND CONVENTIONS

5.1. Hypotheses and Decision Rules

No formal statistical hypothesis test will be performed as this is a descriptive study. A descriptive estimation approach will be used to assess all study objectives regarding safety in the study.

Point estimates and nominal 95% CIs will be provided for all safety endpoints at each planned analysis.

5.2. General Methods

Unless otherwise explicitly stated, descriptive statistics for continuous variables are n, mean, median, standard deviation, minimum, and maximum. Descriptive statistics for categorical variables are the percentage (%) and the numerator (n) and the denominator (N) used in the percentage calculation.

CIs for all endpoints will be presented as 2-sided at the 95% level unless specified otherwise.

For both of the immunogenicity endpoints, the analysis will be primarily based on the evaluable immunogenicity population. **CCI**

All safety and immunogenicity results will also be summarized separately for each age cohort and all participants.

5.2.1. Analyses for Binary Endpoints

Descriptive statistics for categorical variables (eg, proportions) are the percentage (%), the numerator (n) and the denominator (N) used in the percentage calculation, and the 2-sided 95% CIs where applicable. The exact CIs (Clopper-Pearson)¹ for the various proportions of individual groups will be computed using the F distribution.

5.2.2. Analyses for Continuous Endpoints

Unless otherwise stated, descriptive statistics for continuous variables are n, mean, median, standard deviation, minimum, and maximum.

5.2.3. Geometric Mean

For immunogenicity results of serotype-specific OPA titers, the geometric mean will be calculated as the mean of the logarithmically transformed assay results and then exponentiating the mean. The 2-sided 95% CI will be obtained by exponentiating the limits of the CI for the mean of the logarithmically transformed assay results based on Student's t-distribution.

5.2.4. Geometric Mean Fold Rises

The OPA GMFR from before to 1 month after 20vPnC for each age cohort is defined as the geometric mean of the fold rise in the assay results. Only data from participants with nonmissing assay results at both time points will be included in the GMFR calculation.

GMFR will be calculated as the mean difference of the logarithmically transformed assay results (time point after vaccination - before vaccination) and exponentiating the mean difference. The 2-sided 95% CI will be obtained by exponentiating the limits of the CI for the mean difference of the logarithmically transformed assay results based on Student's t-distribution.

CCI

5.3. Methods to Manage Missing Data

A partial AE start date (missing day or missing both month and day) will be imputed by assigning the earliest possible start date using all available information, such as the stop date of the AE and the vaccination date from the same participant, following the Pfizer standard of handling an incomplete AE start date. A complete missing start date for an AE is not allowed in the data collection. The LLOQ for each assay will be provided by Vaccine Research and Development as part of the electronic data transfer or within the Clinical Testing Completion Memo prior to statistical analysis. Assay results above the LLOQ will be reported, and values below the LLOQ, denoted as BLQ, will be imputed as $0.5 \times \text{LLOQ}$ for analysis.

6. ANALYSES AND SUMMARIES

6.1. Primary Endpoints

6.1.1. Local Reactions

6.1.1.1. Main Analysis

- **Estimands:** The percentage of participants reporting prompted local reactions (redness, swelling, and pain at the injection site) within 7 days after vaccination ([Section 2.2](#)).
- **Analysis set:** Safety population among those who report any e-diary data ([Section 4](#)).
- **Analysis time point:** Within 7 days after vaccination.
- **Analysis methodology:** Descriptive statistics.
- **Reporting results:** Count and percentage of participants with the indicated endpoint and the associated 2-sided 95% CI for each and any local reaction after vaccination will be presented by maximum severity across severity levels.

CCI

In addition, the proportions of participants reporting prompted local reactions by maximum severity level, with e-diary errors included, will be provided as a sensitivity analysis.

Figures:

[figure not shown]
Bar charts with the proportions of participants for each local reaction on each day (Day 1 through Day 7) and any day (Day 1 through Day 7) will be plotted, with different patterns displayed in the bar charts for different severity levels for each day and different maximum severity levels for any day.

6.1.2. Systemic Events

6.1.2.1. Main Analysis

- **Estimands:** The percentage of participants reporting prompted systemic events (fever, fatigue, headache, muscle pain, and joint pain) within 7 days after vaccination ([Section 2.2](#)).
- **Analysis set:** Safety population among those who report any e-diary data ([Section 4](#)).
- **Analysis time point:** Within 7 days after vaccination.
- **Analysis methodology:** Descriptive statistics.
- **Reporting results:** Count and percentage of participants with the indicated endpoint and the associated 2-sided 95% CI for each and any systemic event after vaccination will be presented by maximum severity across severity levels.

CCI

6.1.3. Adverse Events

6.1.3.1. Main Analysis

- Estimands: The percentage of participants reporting AEs from vaccination to 1 month after vaccination ([Section 2.2](#)).
- Analysis set: Safety population ([Section 4](#)).
- Analysis time points: Vaccination to 1 month after vaccination.
- Analysis methodology: Descriptive statistics.
- Reporting results: The numerator (n) and the denominator (N) used in the percentage calculation, the percentage (%), and the corresponding 2-sided 95% CI for participants reporting any AE, by system organ class and each preferred term within system organ class, will be presented.

CCI

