4.4. End of Study Definition

The end of the study is defined as the date of the last visit of the last participant in the study.

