8.3.1. Time Period and Frequency for Collecting AE and SAE Information

The time period for actively eliciting and collecting AEs and SAEs (“active collection period”) for each participant begins from the time the participant provides informed consent, which is obtained before the participant’s participation in the study (ie, before undergoing any study-related procedure and/or receiving study intervention), through and including Visit 2.

Follow-up by the investigator continues throughout and after the active collection period and until the AE or SAE or its sequelae resolve or stabilize at a level acceptable to the investigator.

For participants who are screen failures, the active collection period ends when screen failure status is determined.

If the participant withdraws from the study and also withdraws consent for the collection of future information, the active collection period ends when consent is withdrawn.

If a participant permanently discontinues or temporarily discontinues study because of an AE or SAE, the AE or SAE must be recorded on the CRF and the SAE reported using the Vaccine SAE Reporting Form.

Investigators are not obligated to actively seek information on AEs or SAEs after the participant has concluded study participation. However, if the investigator learns of any SAE, including a death, at any time after a participant has completed the study, and he/she considers the event to be reasonably related to the study intervention, the investigator must promptly report the SAE to Pfizer using the Vaccine SAE Reporting Form.

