- Record any AEs on the CRF and on the Vaccine SAE Reporting Form, as applicable and as described in [Section 8.3](#). Record concomitant medications used to treat SAEs.

- Issue the participant a measuring device to measure 20vPnC injection site reactions and a digital thermometer and provide instructions on their use.
- Issue the participant an e-diary (device or application) and provide instructions on its use and completion. Ask the participant to complete the e-diary from Day 1 to Day 7, with Day 1 being the day of vaccination.
- Ask the participant to contact the investigator site staff or investigator as soon as possible during the 7-day postvaccination period if the participant experienced any severe local reactions (eg, redness and/or swelling at the 20vPnC injection site measuring >20 measuring device units [>10 cm], or severe injection site pain [prevents daily activity]) to determine if the event requires further assessment by the investigator (refer to [Section 8.10](#)).
- Ask the participant to contact the investigator site staff or the investigator as soon as possible if they experience any possible Grade 4 prompted local reaction or systemic event within 7 days, after vaccination (refer to [Section 8.10](#)).
- Ask the participant to contact the site staff or investigator immediately if any significant illness or medical event (eg, emergency room visit or hospitalization) occurs.
- Provide the participant with the participant contact card containing the study and investigator information.
- Inform the participant that they may be contacted by site staff to obtain additional information on reports of fever $>102.0^{\circ}\text{F}$ ($>38.9^{\circ}\text{C}$) or Grade 3 events entered into the e-diary.
- Remind the participant to use appropriate contraceptives until 28 days after vaccination, if applicable.
- The investigator or an authorized designee completes the CRF and the source documents and updates the study intervention accountability records.
- The investigator or appropriately qualified designee reviews the e-diary data online at frequent intervals (daily is optimal) for the 7 days (Day 1 is the day of vaccination) following vaccination to evaluate participant compliance and as part of the ongoing safety review.

8.9.2. Visit 2 (28 to 42 Days After Visit 1 [Study Days 29 to 43])

- Record nonstudy vaccinations as described in [Section 6.9](#).

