3.1.3. Adverse Events

AEs will be categorized according to MedDRA terms. AEs will be assessed from the time of informed consent through 1 month after vaccination.

AE reporting will be based on the specific reporting period. Missing AE start dates will be imputed following the Pfizer data standard rules as described in [Section 5.3](#).

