3.1.4. Serious Adverse Events

SAEs will be categorized according to MedDRA terms. SAEs will be collected from the time of informed consent through the end of the study (1 month after vaccination).

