6.1.4. Serious Adverse Events

6.1.4.1. Main Analysis

- Estimands: The percentage of participants reporting SAEs from vaccination to 1 month after vaccination ([Section 2.2](#)).
- Analysis set: Safety population ([Section 4](#)).
- Analysis time point: Vaccination to 1 month after vaccination.
- Analysis methodology: Descriptive statistics.
- Reporting results: The numerator (n) and the denominator (N) used in the percentage calculation, the percentage (%), and the corresponding 2-sided 95% CI for participants reporting any SAEs, by system organ class and each preferred term within system organ class, will be presented.

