6.5.2. Study Conduct and Participant Disposition

6.5.2.1. Participant Disposition

Disposition of participants relative to vaccination will be summarized for all participants as follows: The number and percentage of participants who receive vaccination, complete the 1-month postvaccination visit, and withdraw between vaccination and the 1-month post vaccination visit with specific reasons (participant request, lost to follow-up, AE, protocol violation, other) will be summarized by cohort and overall.

Participants excluded from the safety population will also be summarized along with the reasons for exclusion.

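### Does the undefined end of '1 month after vaccination' leave the primary AE and SAE percentages open to two readings?

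*SAP*

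**What the plan says.** Two of the four primary endpoints are percentages over a period ending 1 month after vaccination. SAP 6.1.3.1 gives "The percentage of participants reporting AEs from vaccination to 1 month after vaccination"; SAP 6.1.4.1 gives "The percentage of participants reporting SAEs from vaccination to 1 month after vaccination". The objectives tables (Protocol 3, SAP 2.2) use the same month without a day count.

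Four other places bear on where the month ends:

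- SAP 3.1.3 states that "AE reporting will be based on the specific reporting period", without defining that period in the visible text.
- SAP 3.1.4 states that "SAEs will be collected from the time of informed consent through the end of the study (1 month after vaccination", the last words standing in brackets as a gloss on the end of the study.
- Protocol 8.3.1 runs active collection from consent "through and including Visit 2". Protocol 8.9.2 gives the timing as "Visit 2 (28 to 42 Days After Visit 1 [Study Days 29 to 43".
- SAP 6.5.2.1 counts participants who "complete the 1-month postvaccination visit".

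Protocol 4.4 defines the end of the study at study level: "The end of the study is defined as the date of the last visit of the last participant in the study".

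**The concern.** The SAP fixes other windows in days. Prompted reactions run from Day 1 to Day 7 (SAP 3.1.1), and the 1-month blood sample must fall 27 to 49 days after vaccination (SAP 4). Nothing comparable is written for AEs and SAEs, and the blood-sample range cannot be borrowed because it governs serology and is wider than the Visit 2 window at both ends.

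An event starting on Study Day 38 in a participant seen on Day 40 would be on the CRF. A programmer applying a 28-, 30- or 31-day cut would leave it out of the primary percentage; one counting to Visit 2 would keep it. SAP 3.1.4 appears to add a third end point, since the study-level end in Protocol 4.4 is not 1 month after vaccination for most participants in a study expected to last about 4 months. If these readings were all live, the primary safety percentages would depend on an unrecorded choice, possibly made after onset dates had been seen.

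**Working it through.** **Step 1: which reading the text supports.**

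| Candidate end | Support | Against |
|---|---|---|
| Visit 2 (Study Days 29 to 43) | Protocol 4.1 and 8.3.1 end collection there; Protocol 8.1 and the synopsis place the visit about 1 month after Visit 1; SAP 6.5.2.1 names a 1-month visit, and no other visit fits; SAP 2.1 declares no departure from the protocol's analysis plan | Never stated outright for the AE and SAE estimands |
| Fixed onset day (28, 30 or 31) | None | Would drop events the protocol actively collects |
| Study-level end (Protocol 4.4) | The words before the bracket in SAP 3.1.4 | The bracket restates it as 1 month after vaccination, a participant-level time; Protocol 8.3.1 stops active collection at Visit 2 |

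Only the first candidate fits all the passages. The conflict between SAP 3.1.4 and Protocol 4.4 is loose wording.

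**Step 2: the plan's own figures.** Protocol Table 4 gives the chance of at least one event as 1 − (1 − p)^N. At p = 0.5% this is 63.3% (N = 200) and 86.5% (N = 400). At 1% it is 86.6% and 98.2%. At 5% both exceed 99.9%. All six entries reproduce. They are stated for a given true rate with no time period attached, so they do not depend on the cut-off.

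**Step 3: how far the percentage could move.** The documents give no AE rate or onset pattern, so the following are assumptions. Let r be the 28-day risk and H = −ln(1 − r). Let a share q of H be spread evenly over time, with the rest falling before day 28. Then for d from 28 to 42 days:

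risk(d) = 1 − exp{−[H(1 − q) + H·q·d/28]}.

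For r = 10%, H = 0.1054.

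- q = 1 (constant hazard): 10.0% at 28 days, 1 − 0.9^(30/28) = 10.7% at 30 days, 1 − 0.9^(31/28) = 11.0% at 31 days.
- q = 1, visits spread evenly over 28 to 42 days: the mean is 1 − (2/H)(0.9 − 0.9^1.5) = 12.3%, or 24.7 of 200 against 20.
- q = 0.25 (most events early), same visit spread: 1 − (8/H)(0.9 − 0.9^1.125) = 10.6%, or 21.2 of 200 against 20.
- Outer limit, constant hazard and every visit on day 42: 1 − 0.9^1.5 = 14.6%.

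For r = 5% the through-Visit-2 figure runs from 5.3% (q = 0.25) to 6.2% (q = 1). For r = 20% it runs from 21.1% to 24.3%.

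**Step 4: scale against sampling error.** The exact (Clopper-Pearson) 95% interval is 6.2% to 15.0% at 20/200 and 7.2% to 13.4% at 40/400. The 12.3% figure lies inside both. The outer limit of 14.6% lies inside the cohort interval but outside the pooled one.

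**The case for a change.** The strongest case for a change is that these percentages are the primary result, that the SAP is where such windows belong, and that one sentence in each of SAP 3.1.3 and 3.1.4 would settle the matter before data are tabulated. A shift caused by a definition is systematic, so lying inside a confidence interval shows that it is small but does not make it sampling error. The visible text also gives no rule for a Visit 2 that is missed or out of window. Under the Visit 2 reading, in-window follow-up varies from 28 to 42 days (42/28 = 1.5-fold), and no visible table summarises it.

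Part of this stands. The visible text does lack an explicit definition, and writing Visit 2 into SAP 3.1.3 and 3.1.4 would be a harmless tidying step. Three considerations limit its weight:

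- Such a sentence would only record the reading the documents already lead to.
- The unequal follow-up comes from the 28-to-42-day visit window itself, and clearer wording would not remove it.
- A fixed cut-off is a debatable preference. It would take collected events out of the primary percentage, and it might need a protocol amendment if judged a major modification (Protocol 9, SAP 2).

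For missed or late visits there is a workable default: count what was recorded on or after vaccination during the active collection period. A redacted block also follows SAP 6.1.3.1, so the absence can be asserted only for the visible text.

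**Conclusion.** No change to the plan follows. The end of the AE and SAE period is not spelled out, but read together the two documents lead to Visit 2. Neither a fixed day nor the study-level end is a serious rival.

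Under the stated assumptions (28-day risk of 10%, visits spread evenly over the window), counting through Visit 2 instead of stopping at day 28 adds about 1 to 5 participants per cohort of 200. The lower end applies if most events fall early. The true rate, onset pattern and visit spread are unknown, so this shows scale only and is not a forecast.

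Nothing is tested in this single-arm study (Protocol 9.1, SAP 5.1), so no error rate, decision rule or sample size depends on the choice. Either reading gives a usable descriptive percentage, and no conclusion would be unsound without the added sentence.
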